### 8.4.2 BASELINE DESCRIPTIVE STATISTICS

The study and reference groups will be compared on baseline characteristics, including demographics and disease status, using descriptive statistics without inferential statistics (there are no associated hypotheses).

#### 8.4.3 ANALYSIS OF THE PRIMARY OUTCOME MEASURE(S)

The statistical analysis plan is outlined in detail in the Target Vs. Emulated Trial Table in Section 1.2. We do not anticipate substantive missing data.

#### 8.4.4 ANALYSIS OF THE SECONDARY OUTCOME MEASURE(S)

No secondary endpoints are dependent on the findings from the primary endpoint. Analysis methods will follow the general approach for the primary outcome. Specifically, steps 1-4 of the Target Vs. Emulated Trial Table in Section 1.2 produce weights which reflect probability of ultrasound adherence. These weights will then be used to fit inverse probability weighted regression models. Correspondingly, results will be presented as risk differences or odds ratios with appropriate 95% confidence intervals.

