## 3 OBJECTIVES AND ENDPOINTS

PRIMARY PURPOSE (OBJECTIVES)	OUTCOME MEASURES	JUSTIFICATION FOR OUTCOME MEASURES
Primary		
Estimate whether all-cause mortality in patients with an incidental thyroid nodule on PET-CT who did not have thyroid ultrasound within 3 months was non-inferior within a 5% margin to those who did have ultrasound.	All-cause mortality	Determined by three thyroid endocrinologists and a head and neck surgeon to be a reasonable timeframe in which thyroid cancers have time to develop and contribute to mortality but not so much that it becomes difficult to separate thyroid cancer-related mortality from other causes.
Secondary		
Estimate whether incidence rates of thyroid cancers, thyroid ultrasounds, thyroid biopsies, and thyroid surgeries are higher in patients with an incidental thyroid nodule on PET-CT who had versus did not have thyroid ultrasound within 3 months.	incidence rate of thyroid cancers, incidence rate of thyroid ultrasounds, incidence rate of thyroid biopsies, incidence rate of thyroid surgeries	Between-group differences in these outcomes will help establish whether the estimated non-inferiority result is clinically meaningful and justifiable due to increased morbidity in those who under further thyroid nodule characterization.
Tertiary/Exploratory		
Explore whether types of thyroid cancer diagnoses are different among patients with an incidental thyroid nodule on PET-CT who had versus did not have thyroid ultrasound within 3 months.	Thyroid cancer subtypes	It is likely that mostly indolent papillary thyroid carcinomas are identified when incidental thyroid nodules are further evaluated.

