### **Explanation**

Exposure: 1 = thyroid ultrasound performed within 3-months following imaging examination; 0 = thyroid US not performed within 3-months following imaging examination

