### **Explanation**

Primary Outcome Binary: 1 = died within follow-up period; 0 = did not die within follow-up period

follow\_up\_in\_days

Primary Outcome Continuous: Number of days from imaging examination to death, 10-years, or end of study, whichever comes first

thyroid\_cancer\_dx\_post\_pet

Secondary Outcome Binary: 1 = ICD10 C73 diagnosis after PET exam; 0 = no ICD10 C73 diagnosis

post\_pet\_thyroid\_excision

Secondary Outcome Binary: 1 = CPT code 60100 for thyroid excision performed after PET exam

thyroid\_ultrasounds

Secondary Outcome Continuous: Number of thyroid ultrasound exams performed after PET exam

thyroid\_biopsies

Secondary Outcome Continuous: Number of thyroid biopsies performed after PET exam

thyroid\_cancer\_subtype

Exploratory Outcome: ICD10 C73 subcategory

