## Secondary Outcome Measure(s)

Hypotheses: Incidence rate ratios of (1) thyroid cancer diagnoses, (2) thyroid ultrasounds, (3) thyroid biopsies, and (4) thyroid surgeries are each higher in patients with an incidental thyroid nodule on PET-CT who had versus did not have thyroid ultrasound within 3 months.

Null hypotheses: Incidence rate ratios of (1) thyroid cancer diagnoses, (2) thyroid ultrasounds, (3) thyroid biopsies, and (4) thyroid surgeries are each not  $>1$  in patients with an incidental thyroid nodule on PET-CT who had versus did not have thyroid ultrasound within 3 months.

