## 8.4 STATISTICAL ANALYSES

### 8.4.1 GENERAL APPROACH

For descriptive statistics, categorical data will be presented, stratified by observed treatment status, as percentages while continuous data will be presented as medians and interquartile ranges. For non-inferiority (primary aim) inferential tests, statistical significance is defined as the estimated 7-year mortality two-sided confidence interval of the study group not crossing an absolute 5% lower 7-year mortality rate of the reference group. For superiority (secondary aims) inferential tests, statistical significance is defined as the estimated between-group difference two-sided confidence interval not crossing zero.

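### The ultrasound hypothesis is met nearly by construction, and the secondary hypotheses, variables, effect measures and decision rule do not match

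*Combined protocol and SAP*

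**What the plan says.** **Exposure and ultrasound outcome.** Section 7 codes the exposure as "1 = thyroid ultrasound performed within 3-months following imaging examination" and defines the outcome `thyroid_ultrasounds` as "Number of thyroid ultrasound exams performed after PET exam". No section takes the exposure scan out of the count. In Section 1.2, step 2 of the emulation censors a no-ultrasound clone when a scan is done, and an ultrasound clone at 3 months if none has been done.

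**Hypotheses and measures.** Section 3 lists "incidence rate of thyroid cancers, incidence rate of thyroid ultrasounds, incidence rate of thyroid biopsies, incidence rate of thyroid surgeries". Section 8.1 hypothesises "Incidence rate ratios of (1) thyroid cancer diagnoses, (2) thyroid ultrasounds, (3) thyroid biopsies, and (4) thyroid surgeries are each higher in patients" who had the ultrasound; its null is "Incidence rate ratios of (1) thyroid cancer diagnoses, (2) thyroid ultrasounds, (3) thyroid biopsies, and (4) thyroid surgeries are each not" above 1. For the analysis, Section 8.4.4 says "These weights will then be used to fit inverse probability weighted regression models", without naming a model family, link or offset, and then "results will be presented as risk differences or odds ratios with appropriate 95% confidence intervals". The decision rule for secondary aims in Section 8.4.1 is that "statistical significance is defined as the estimated between-group difference two-sided confidence interval not crossing zero".

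**Time and coding.** Section 1.2 sets the secondary window at 7 years from PET or study end. The Section 7 secondary variables carry no window: cancer and excision are yes/no flags, and ultrasounds and biopsies are totals, all simply after the PET. Section 1.2 lists a number of surgeries.

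**The concern.** A scan that defines the arm should not also count as evidence that the arm leads to more scans. If it does, the test reports the definition of the exposure and says nothing about downstream use.

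The second problem is that a hypothesis, the variable that measures it, the effect measure and the rejection rule should all be on one scale. Here the hypothesis is a rate ratio with null 1, two variables are counts and two are flags, the reported measures are for binary outcomes, and the only stated criterion is zero. An analyst would have to invent the link between them after seeing the data.

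These outcomes carry weight. Section 3 uses them to help establish whether a non-inferiority result is clinically meaningful, and Section 4.1 allows the margin to be reconsidered in the light of the secondary benefits.

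**Working it through.** The documents give no sample size, power or expected effect for any secondary outcome, so there is no planned figure to reproduce.

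**1. Ultrasound ratio with no downstream effect.** Let *r* be the mean number of scans per patient after month 3, the same in both arms, with equal person-time. The documents give no value, so *r* is assumed. The ultrasound arm contributes the exposure scan plus *r*; the comparator contributes 0 in the grace period plus *r*. The planned ratio is (1 + *r*)/*r*:

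- *r* = 0.3: 1.3/0.3 = 4.3
- *r* = 0.5: 1.5/0.5 = 3.0
- *r* = 1.0: 2.0/1.0 = 2.0

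The same check as a yearly rate λ over follow-up *T*, without deaths, is [1 + λ(*T* − 0.25)]/[λ(*T* − 0.25)]:

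| λ per year (assumed) | *T* = 7 y | *T* = 3.79 y |
|---|---|---|
| 0.02 | 8.41 | 15.12 |
| 0.05 | 3.96 | 6.65 |
| 0.1 | 2.48 | 3.82 |
| 0.2 | 1.74 | 2.41 |
| 0.5 | 1.30 | 1.56 |

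Counted only after month 3, the ratio is *r*/*r* = 1.00 in every row.

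Two things limit this. If a share *d* of ultrasound-arm clones dies unscanned within 3 months, the ratio becomes (1 − *d* + *r*)/*r*; with an assumed *d* = 0.1 and *r* = 0.5 it is 1.4/0.5 = 2.8. With unequal later means *r*₁ (ultrasound) and *r*₀ (comparator) and no early deaths, the ratio is at or below 1 only if *r*₀ ≥ 1 + *r*₁, that is, if the comparator later averages at least one more scan per patient.

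**2. Effect measure.** A risk difference or odds ratio needs a binary outcome. Cancer and excision are binary in Section 7. Ultrasounds and biopsies are counts, and no cut is defined. For binary outcomes, compare the odds ratio with the rate ratio ln(1 − *p*₁)/ln(1 − *p*₀):

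- Rare outcome, assumed risks 1.1% v 0.55%: odds ratio 2.01, rate ratio 2.01.
- Biopsy as ever/never, 26% (the share of nodules recommended for biopsy, Section 2.2) v an assumed 5%: risk ratio 5.2, rate ratio 5.9, odds ratio 6.7, risk difference 21 points.

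The choice hardly matters when events are rare, but it does for biopsy.

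**3. Zero criterion.** Assume 1,000 per arm and 3% events in each. The log odds ratio is 0 with SE √(1/30 + 1/970 + 1/30 + 1/970) = 0.262. On the log scale the 95% interval is −0.51 to 0.51, which contains 0. On the odds-ratio scale it is 0.60 to 1.67, which contains 1 but can never contain 0. Zero therefore suits a difference or a log ratio, not an untransformed odds ratio.

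**4. Observation time.** Scans run from 1 January 2015 to 31 December 2021 (Section 5.1); data end on 15 October 2025 (Section 4.3). The last scan has 3.79 years of potential follow-up. Scans after 15 October 2018 cannot reach 7 years: 1,173 of 2,557 accrual days, or 46%. Within the Section 1.2 window, potential follow-up is 3.79 to 7 years, a spread of 3.2 years. Totals and flags need a denominator or censoring to allow for this.

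**5. Unequal mortality.** With event rate *l* equal in both arms and death rate *m* = −ln(1 − *M*)/7, the 7-year cumulative incidence is *l*/(*l* + *m*) × [1 − exp(−7(*l* + *m*))]. All inputs are assumed:

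- *M* = 30% v 35%, *l* = 0.002: 1.17% v 1.13%, odds ratio 1.04.
- *M* = 30% v 35%, *l* = 0.05: 25.1% v 24.3%, odds ratio 1.04.
- *M* = 25% v 45%: odds ratio 1.16 (*l* = 0.002) and 1.19 (*l* = 0.05).

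**The case against.** The best defence is that Section 8.4.4 does not stand alone. It says the methods follow the primary approach, whose step 2 censors person-time and whose step 4 models the outcome over time. Section 1.2 supplies a window, Section 6.3 has a loss-to-follow-up rule for secondary outcomes, and Section 7 has a follow-up variable in days. Cloning also puts every patient in both arms, so scan dates start balanced. The zero rule refers to a between-group difference, and a risk difference is the first measure that Section 8.4.4 offers. Total scans is a fair description of what a strategy consumes.

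Much of this stands, and it rules out some stronger readings that a reader might infer:

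- *That no secondary hypothesis can be tested.* The exposure overlap affects one outcome of four. For cancer and surgery, a risk difference against 0 tests the same direction as a ratio against 1.
- *That the plan chose to ignore time.* It is under-specified: the window and person-time logic exist elsewhere but are not carried into the secondary variables or models. The follow-up variable is labelled for the primary outcome and runs to 10 years.
- *That follow-up differs by up to 7 years.* That takes the Section 7 variables as uncapped (10.79 − 3.79 = 7.0). The Section 1.2 window reduces it to 3.2.
- *That every ultrasound-arm clone has at least one scan.* Those who die unscanned before month 3 stay in the arm with none.
- *That any odds ratio would be declared significant.* This needs a difference rule applied to an untransformed ratio. The text leaves the ratio criterion unstated.

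The defence does not answer the remaining points. The exposure scan is in a tested outcome, and nothing says how rate-ratio hypotheses about counts are to be answered with risk differences or odds ratios.

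**Conclusion.** The point holds in this form. The ultrasound hypothesis is met nearly by construction: the planned ratio is about 4.3, 3.0 or 2.0 when later use is identical at an assumed 0.3, 0.5 or 1.0 scans per patient, and lower to the extent that ultrasound-arm clones die unscanned in the grace period. These sizes depend on the assumed rates; the direction does not, unless the comparator later catches up by about a full scan per patient.

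Separately, for all four outcomes the hypothesis (rate ratio, null 1) does not match the reported measure (risk difference or odds ratio) or the stated criterion (zero). This is most serious for the two counts, where the reported measures are undefined. For cancer and surgery the mismatch is mainly one of scale. Distortion from unequal mortality is small unless survival differs widely between arms. The surgery flag against a stated number is a minor inconsistency. The plan should be corrected before the secondary analyses are run.

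**What to change.** 1. **Ultrasounds:** test the hypothesis on scans after the 3-month grace window, in both arms. Report total scans descriptively.
2. **Ultrasound and biopsy counts:** specify a weighted rate model (Poisson or negative binomial) with a log person-time offset over the Section 1.2 window and a bootstrap interval, judged against 1. State how death and the Section 6.3 loss-to-follow-up rule end person-time.
3. **Cancer and surgery:** use weighted 7-year cumulative incidence with death as a competing event, reporting the risk difference (null 0) and risk ratio (null 1), and restate their hypotheses on that scale. Define surgery as a first dated event, or count surgeries if a number is wanted.
4. **Alignment:** give the Section 7 secondary variables the Section 1.2 window, and make Sections 8.1, 8.4.1 and 8.4.4 name the same measure and null for each outcome.

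The cost is SAP wording and modest programming, provided that event dates can be extracted for biopsy and surgery, which the documents do not state. The ultrasound effect will look smaller, because the exposure scan no longer counts towards it.

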	
Kaplan-Meier to estimate probability of mortality in each arm
 
Construct a 95% confidence interval for the absolute difference between the two arms, <math>\Delta_{RD}</math>
 
Taking the type I error rate, alpha, to be 0.05, non-inferiority is concluded if the upper limit of a two-sided 90% = 100(1-2alpha)% confidence interval for <math>\Delta_{RD}</math> is less than the prespecified margin.
	
baseline; one clone assigned to each treatment strategy.
 
2. Person-time for each clones is censored when their observed treatment strategy is non-adherent. That is, clones assigned to undergo thyroid ultrasound within 3 months are censored at 3 months of follow-up if no ultrasound is performed. Similarly, clones assigned to not undergo an ultrasound within 3 months are censored at the time an ultrasound is performed.
 
3. A pooled logistic regression model is fit for the (conditional) probability of adherence, adjusting for a priori specified baseline factors that predict adherence.
 
4. A marginal structural pooled logistic regression model is fit to the mortality outcome data, as a function of time and treatment (with interaction), using inverse-probability of censoring weights from step 3.
 
5. Treatment-specific marginal probabilities of all-cause mortality are estimated from the fit in step 4, from which the causal risk difference, <math>\Delta_{RD}</math>, is estimated along with a two-sided 90% = 100(1-2alpha)% confidence interval (constructed via the bootstrap).
 
6. Taking the type I error rate, alpha, to be 0.05, non-inferiority is concluded if the upper limit of a two-sided 90% = 100(1-2alpha)% confidence interval for <math>\Delta_{RD}</math> is less than the prespecified margin.

Secondary Outcomes	
Cumulative over 7-years from PET:
 
Number of thyroid cancers
 
Number of thyroid ultrasounds
	
Cumulative incidence rate over 7-years from PET or to the end of the study period

	Number of thyroid biopsies Number of thyroid surgeries	
Exploratory Analysis	Types of thyroid cancer diagnoses	Same

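### The secondary hypotheses are incidence rate ratios against 1, but Section 8.4.4 reports only risk differences or odds ratios, which do not fit the two count outcomes, and Section 8.4.1 gives a null only for differences

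*Combined protocol and SAP*

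**What the plan says.** Four parts of the combined protocol and SAP define the secondary comparison.

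- **Hypotheses (Section 8.1).** "Incidence rate ratios of (1) thyroid cancer diagnoses, (2) thyroid ultrasounds, (3) thyroid biopsies, and (4) thyroid surgeries are each higher in patients" who had the ultrasound. The matching nulls are that each ratio does not exceed 1.
- **Outcome measures (Sections 3 and 1.2).** Section 3 lists "incidence rate of thyroid cancers, incidence rate of thyroid ultrasounds, incidence rate of thyroid biopsies, incidence rate of thyroid surgeries". The emulation column of the Section 1.2 table gives "Cumulative incidence rate over 7-years from PET or to the end of the study period".
- **Analysis (Section 8.4.4).** Methods follow the general approach for the primary outcome and use weights from the clone-censor steps: "These weights will then be used to fit inverse probability weighted regression models". Then "results will be presented as risk differences or odds ratios with appropriate 95% confidence intervals". No model family, link or person-time term is named, and no measure is tied to any of the four outcomes.
- **Decision rule (Section 8.4.1).** For the secondary aims, "statistical significance is defined as the estimated between-group difference two-sided confidence interval not crossing zero".

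Section 7 fixes the data types. Thyroid cancer and thyroid excision are 0/1 variables. Ultrasounds are "Secondary Outcome Continuous: Number of thyroid ultrasound exams performed after PET exam", and biopsies are defined in the same way.

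**The concern.** The hypotheses are on one scale, the reported estimates on two others, and the decision rule covers only one of those two. An analyst who follows Section 8.4.4 as written produces no estimate on the scale of Section 8.1. For ultrasounds and biopsies, the analyst must also first make an unplanned decision to reduce counts to any or none. Because risk difference and odds ratio are offered as alternatives with no allocation to outcomes, the measure could be chosen after the results are known.

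Section 3 gives these outcomes a specific job: they are meant to show whether a non-inferior mortality result is clinically worthwhile, because further work-up carries morbidity. Repeat ultrasounds and biopsies are part of that burden, and an any-or-none measure does not see them.

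**Working it through.** The documents state no event rate, sample size or power for any secondary outcome, so there is no planned figure to reproduce. The check sets the sections side by side and sizes the mismatch with assumed inputs.

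**1. Scale and null, by outcome**

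| Outcome | Coding (Section 7) | Hypothesis (8.1) | Reported measure (8.4.4) | Null given for that measure (8.4.1) |
|---|---|---|---|---|
| Thyroid cancer | 0/1 | rate ratio, 1 | risk difference or odds ratio | 0 for a difference; none for a ratio |
| Surgery | 0/1 | rate ratio, 1 | same | same |
| Ultrasounds | count | rate ratio, 1 | same; fits only after a cut to any/none | same |
| Biopsies | count | rate ratio, 1 | same; fits only after a cut to any/none | same |

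**2. What a cut to any/none does to a rate ratio of 2.** Assume Poisson counts with mean m in the reference group and 2m in the other. The probability of any event is p = 1 − exp(−mean), so the odds are exp(mean) − 1. The odds ratio is then [exp(2m) − 1]/[exp(m) − 1] = exp(m) + 1, and the risk difference is exp(−m) − exp(−2m).

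| Assumed m | True rate ratio | Any-event odds ratio | Any-event risk difference |
|---|---|---|---|
| 0.02 | 2 | 2.02 | 0.019 |
| 0.1 | 2 | 2.11 | 0.086 |
| 0.5 | 2 | 2.65 | 0.239 |
| 1.0 | 2 | 3.72 | 0.233 |

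The odds ratio tracks the rate ratio only when events are rare. The risk difference is almost the same at m = 0.5 and m = 1.0, although the absolute excess in procedures per patient has doubled from 0.5 to 1.0.

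**3. First events (thyroid cancer, surgery).** With constant rates and equal follow-up, the rate ratio is ln(1 − p1)/ln(1 − p0). For assumed risks of 2% v 4% it is ln(0.96)/ln(0.98) = 2.02, against an odds ratio of 2.04. For 10% v 20% it is 2.12 against 2.25, and for 30% v 60% it is 2.57 against 3.5. At low risks the difference is negligible.

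**4. The ultrasound outcome.** Under step 2 of Section 1.2, an ultrasound-arm clone with no ultrasound is censored at 3 months. Every clone still followed in that arm after month 3 has therefore had at least one. The outcome variable counts exams after the PET and does not exclude the qualifying one. An any/none proportion in that arm is thus 1, apart from clones who die within the 3 months without an ultrasound.

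Counting exams does not cure this by itself. Suppose both arms have the same mean number m of further ultrasounds over the same person-time, and ignore deaths in the grace period. The ratio is then about (1 + m)/m: 11 at m = 0.1, 3 at m = 0.5 and 2 at m = 1.0, with no downstream effect at all.

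**5. Follow-up.** Section 4.3 gives 15 October 2025 as the mortality cut-off; its use for the secondary outcomes is my assumption. The last eligible PET (31 December 2021) then has 3.79 years. Of 2,557 accrual days, 1,384 fall on or before 15 October 2018, so PETs on the other 1,173 days (45.9% of days, not necessarily of patients) cannot reach 7 years. An ever/never proportion that ignores time would not be a 7-year quantity.

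**The case against.** Four arguments favour the plan, and each has some force.

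*The zero rule is sound where it applies.* Section 8.4.1 speaks of a between-group difference, and zero is the right null for one. It also works for counts: in simulations with assumed Poisson means and 500 per arm, a rate difference judged against 0 gave 5.2% type I error and 76.0% power (0.4 v 0.3), against 5.1% and 75.8% for a rate ratio judged against 1. This stands. The difficulty with the counts lies in the measures named in Section 8.4.4, not in the null of zero.

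*A reader might infer that the rule passes every odds ratio.* An odds-ratio interval lies wholly above zero, so a rule of zero would always be met. The documents do not support that reading. The rule is confined to differences, and where Section 8.2 tests an odds ratio it works on the log-odds scale, on which zero is the correct null for no effect. What is missing is a stated null for ratios.

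*The binary outcomes lose little.* For a 0/1 outcome, a risk difference of 0 and an odds ratio of 1 are the same null, and with equal follow-up and constant rates so is a rate ratio of 1. It would therefore be too strong to say that none of the four hypotheses can be tested.

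*Time may already be handled.* Section 8.4.4 invokes the primary approach and cites steps 1-4, and step 4 is a pooled logistic model in time. If that model carries over, unequal follow-up is dealt with for first events, and its per-interval odds ratio would be close to a rate ratio when events are uncommon in each interval. The text does not say whether it carries over. Step 4 also includes a treatment-by-time interaction, so no single ratio results, and it does not extend to repeated counts.

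**Conclusion.** The mismatch is real and in the current text. Section 8.4.4 yields no estimate on the rate-ratio scale of Section 8.1, does not say which measure goes with which outcome, and has no direct measure for the two counts. Section 8.4.1 leaves odds ratios and rate ratios without a decision rule.

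The size depends on event frequency, which the documents do not give. It is negligible for rare first events (2.04 v 2.02 at assumed risks of 2% and 4%) and material for common repeated procedures (3.72 v 2 at an assumed mean of 1.0). The ultrasound outcome is affected most, because the exposure counts towards its own outcome.

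A reader might also infer that the ultrasound odds ratio is infinite. That does not follow: the plan states no cut to any/none, and ultrasound-arm clones who die before month 3 without an ultrasound are not artificially censored, so the proportion need not be 1. The result is largely fixed by design, which is enough to require a change. This should be corrected before analysis; it does not touch the primary mortality comparison.

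**What to change.** **Section 8.4.4**

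- *Ultrasounds and biopsies (counts):* fit the weighted clones with a Poisson or negative-binomial model, with log person-time to death, artificial censoring or end of follow-up as offset. Report the rate ratio with a patient-level bootstrap 95% interval, judged against 1.
- *Ultrasounds:* state that the qualifying ultrasound is not an outcome, for example by counting only exams after the 3-month grace period in both arms, with person-time starting at the same point.
- *Thyroid cancer and surgery (0/1):* report the first-event rate ratio judged against 1, with the weighted 7-year risk difference judged against 0 as a supplement.

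**Section 8.4.1.** Replace the zero rule for the secondary aims with an interval that excludes 1 for ratios and 0 for differences. As the hypotheses in Section 8.1 are directional, say also that support requires the interval to lie on the hypothesised side.

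Then align Sections 8.1, 8.4.1 and 8.4.4, so that each outcome has one primary measure, one model and one null.

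**Cost.** SAP wording and a different regression call. Event dates are needed for first-event person-time and to separate the qualifying ultrasound from later ones; Section 7 lists counts and 0/1 flags for these outcomes, so the dates must be kept at extraction.
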